## 1. Glossary

BA	Behavioural Activation
CASPER	Collaborative Care in Screen-Positive Elders
CASPER Study	Study designed to assemble an epidemiological cohort of people over 65 years of age
CASPER Cohort	Cohort of participants over 65 years of age who consented to be followed up as part of the CASPER Cohort
CASPER Trial	Trial using CASPER Cohort participants with sub-threshold depression who consented to take part in the CASPER trial
CASPER PLUS Trial	Trial using CASPER Cohort participants with above-threshold depression who consented to take part in the CASPER PLUS trial
CC	Collaborative Care
CONSORT	Consolidated Standards of Reporting Trials
CRF	Case Report Form
IAPT	Improving Access to Psychological Therapies
ITT	Intention-to-treat
MINI	Mini-International Neuropsychiatric Interview (Major Depressive Episode Module used in this study)
NICE	National Institute for Health and Care Excellence
NSAE	Non-Serious Adverse Event
PC-MIS	Patient Case Management Information System
SAE	Serious Adverse Event
SAP	Statistical Analysis Plan
SOP	Standard Operating Procedure

## 2. Introduction

### The CASPER Study

The CASPER study has been designed to assemble an epidemiological cohort of people over 65 years of age (the CASPER Cohort), from which those eligible to participate in a trial of collaborative care for sub-threshold depression (the CASPER Trial including an internal pilot) and a trial of collaborative care for above-threshold depression (the CASPER PLUS Trial) were identified.

### Research Objectives

#### CASPER Pilot Trial

1. To develop a low intensity collaborative care intervention based upon evidence-supported models of care for elderly people with screen-positive sub-threshold depression
2. To establish the acceptability and uptake of this service by elderly people with screen-positive sub-threshold depression in primary and residential care settings
3. To test the feasibility of conducting a successful trial of low intensity collaborative care intervention for elderly people with screen-positive sub-threshold depression
4. To validate the Whooley questions in a UK elderly population

#### CASPER Trial

5. To establish the clinical effectiveness of a low intensity collaborative care intervention for elderly people with screen-positive sub-threshold depression
6. To examine the cost effectiveness of a low intensity collaborative care intervention for elderly people with screen-positive sub-threshold depression across a range of health and social care costs

#### CASPER PLUS Trial

7. To establish the clinical effectiveness of a low intensity collaborative care intervention for elderly people with screen positive above-threshold depression
8. To examine the cost effectiveness of a low intensity collaborative care intervention for elderly people with screen positive above-threshold depression

### Scope of Statistical Analysis Plan

This analysis plan exclusively covers details of the statistical analysis of treatment efficacy in the CASPER Trial: To establish the clinical effectiveness of low intensity collaborative care intervention for elderly people with screen-positive sub-threshold depression (Research Objective 5). Any analyses addressing the trial pilot objectives, the qualitative evaluation and economic analysis as well as any further planned analyses of data from CASPER Cohort participants including the CASPER PLUS trial are detailed elsewhere.

### 3. Trial Design

#### Summary

The CASPER trial is a 2-arm, unblinded, pragmatic randomised controlled trial with randomisation at the patient level. The two arms are:

(1) Collaborative Care with Behavioural Activation (CC)

- Customised low intensity care programme delivered to an established protocol by a case manager (mental health / IAPT worker)
- 8-10 weekly sessions, first session conducted face to face, subsequent sessions fact to face or by telephone according to patient preference
- Elements of CC: telephone support, symptom monitoring and active surveillance, low intensity psycho-social management / behavioural activation

(2) Usual Primary Care (UC)

- GP delivered usual care management of sub-threshold depression in line with NICE guidance

Full details of the background and design of the trial are given in the study protocol (latest version at time of writing: Version 2.8, 3 Dec 2013).

#### Sample Size

To detect a minimum standard effect size of 0.3 with 80% power and a two-sided 5% significance level would require 352 patients (176 in each group). Although this is an individually-randomised trial, there may be potential clustering at the level of each collaborative care case manager and hence the sample size was inflated to account for this. Based upon an ICC = 0.02 and a caseload size of 20, the design effect would be 1.38 ( $1 + (20 - 1) \times 0.02$ ) and 486 patients (243 in each group) would be required.

The original trial sample size allowed for 10% loss to follow-up, resulting in a total of 540 patients (270 in each group). Following the inspection of interim recruitment figures and disproportionate dropout from the collaborative care arm, this assumption was revised (Substantial Amendment 17). Allowing for a loss to follow-up of 26%, the final sample size needed is 658 patients (329 in each group).

#### Randomisation

Participants with sub-threshold depression who met the inclusion criteria, provided written consent and were not actively receiving psychological therapy were eligible for randomisation into the trial. Once invitation, baseline and diagnostic interview data were collected and entered into the study database, randomisation was carried out by the York Trials Unit Randomisation Service. Participants were randomised on a 1:1 basis using simple randomisation to either the intervention group (collaborative care) or control group (usual care).

## **Blinding**

Blinding of the participants was not feasible, nor was blinding of all members of the study team who were actively involved in the administration of the study. However, the trial statistician responsible for the final statistical analysis will be kept blind to group allocation until the primary analysis has been completed and checked by the second statistician. Some of the trial data explicitly reveal treatment allocation (e.g. intervention details and patient comments), therefore analysis and reporting following the primary analysis will be unblinded.

## **Follow-up**

Follow-up was at 4 and 12 months post-randomisation by postal questionnaire for all participants who consented to participate in the trial. If non-returned, a reminder letter and second questionnaire pack were sent 21 days following the original mailing date. If the questionnaire was not returned after 35 days, some participants were called in person.

## **4. Outcomes**

### **Primary Outcome**

The primary outcome of the CASPER trial is Depression Severity and Symptomatology (PHQ-9) at 4 months post-randomisation.

#### *PHQ-9*

The PHQ-9 is a nine item depression scale. Each item is scored between 0 and 3, thus PHQ-9 scores can range from 0 to 27 with higher scores indicating greater depression. Up to two missing questionnaire items are pro-rated, and no total scores are calculated for responses with more than two missing items. Scores of 5, 10, 15, 20 have been used as cut points for mild, moderate, moderately severe and severe depression.

### **Secondary Outcomes**

- Depression severity and symptomatology at 12 months (PHQ-9)
- Binary Depression Severity at 4 & 12 months (PHQ-9), using scores  $\geq 10$  to designate moderate depression caseness
- Quality of Life at 4 & 12 months (SF-12 and EQ-5D)
- Psychological Anxiety at 4 & 12 months (GAD-7)
- Mental Health Medication at 4 & 12 months
- Mortality at 4 & 12 months

#### *SF-12*

The SF-12 is a generic health status measure and a short form of the SF-36 health survey. It consists of 12 questions measuring 8 domains (Physical, Role Physical, Bodily Pain, General Health, Vitality, Social Functioning, Role Emotional and Mental Health) rated over the past month. Questions have 3 or 5 response categories, and responses are summarised into a physical and mental component

score (PCS and MCS). Outcomes range from 0 (lowest level of health) to 100 (highest level of health).

#### *EQ-5D*

The EQ-5D is a standardised measure of current health status developed by the EuroQol Group for clinical and economic appraisal. The EQ-5D consists of five questions, each assessing a different quality of life dimension (Mobility, Self-care, Usual activities, Pain/Discomfort and Anxiety/Depression). Each dimension is rated on three levels: no problems (score=1), some problems (score=2) and extreme problems (score=3). A weighted summary index can be derived to give a score between 1 (perfect health) and 0 (death). For the purpose of the present analysis, only scores of the individual dimensions will be utilised. The summary index will be analysed separately as part of the cost utility analysis.

#### *GAD-7*

The GAD-7 is a brief measure of symptoms of anxiety, based on diagnostic criteria described in DSM-IV. It consists of seven questions and is calculated by assigning scores of 0, 1, 2, and 3, to the response categories of "not at all", "several days", "more than half the days," and "nearly every day," respectively. GAD-7 total score for the seven items ranges from 0 to 21. Scores of 5, 10, and 15 represent cut points for mild, moderate, and severe anxiety, respectively.

#### *Mental Health Medication*

Medication data was captured by self-report on the follow-up questionnaires. Participants indicated any prescribed medication by selecting from a list of ten anti-depressants. Independent objectively collected medication data from GP records will not be included here and will be incorporated in the economic analysis.

#### *Mortality*

Mortality was established by flagging all randomised participants to the NHS Information Centre at regular intervals. Members of the research team recorded any identified deaths on the study management database.

### **Other Collected Data**

- Demographic details at invitation
- Whooley Questions at invitation and baseline
- Questions about physical health problems at baseline
- Questions about falls at baseline
- PHQ-9 at diagnostic interview
- M.I.N.I. (Major depressive episode module) at diagnostic interview
- PHQ-15 at baseline, 4 & 12 months
- CD-RISC 2 at baseline, 4 & 12 months
- Adverse events (as arising up to 12 months follow-up)
- Economic Evaluation at baseline, 4 & 12 months

### *Demographics*

Patients completing the background information questionnaire following their invitation provided demographic details regarding age, gender, ethnicity, level of education as well as smoking and alcohol consumption habits.

### *Whooley Questions*

The Whooley questions comprise two questionnaire items that form a brief depression screening tool. The questions are: 1. "Over the past month, have you been bothered by feeling down, depressed or hopeless?" and 2. "Over the past month, have you been bothered by having little interest or pleasure in doing things?". Response options are Yes or No.

### *Physical Health Problems*

Participants were asked to indicate whether they suffer from any of a list of ten selected health problems (Diabetes, Osteoporosis, High blood pressure, Rheumatoid arthritis, Osteoarthritis, Stroke, Cancer, Respiratory conditions, Eye conditions, Heart disease) or give details of any other health problems.

### *M.I.N.I.*

The 9-item major depressive episode module of the Mini International Neuropsychiatric Interview was used to ascertain the presence or absence of depressive symptoms and categorise participants into non-depressed, sub-threshold depressive symptoms or major depressive episode groups. The nine items comprised: 1) Depressed mood, 2) Loss of interest, 3) Significant weight loss or gain or decrease or increase in appetite, 4) Insomnia or hypersomnia, 5) Psychomotor agitation or retardation, 6) Fatigue or loss of energy, 7) Feelings of worthlessness or excessive or inappropriate guilt, 8) Diminished ability to think or concentrate, or indecisiveness, 9) Recurrent thoughts of death, recurrent suicidal ideation without a specific plan, or suicide attempt or a specific plan.

### *Falls*

Participants were asked in two questions whether and how often they had fallen in the past 12 months.

### *PHQ-15*

The PHQ-15 is a 15-item physical health problems questionnaire. Each health issue is rated as 0 (not bothered), 1 (bothered a little) or 2 (bothered a lot). Items are added to form a scale from 0 to 30, higher scores indicating worse symptom severity. Scores of 5, 10 and 15 have been used as cut-offs for low, medium and high symptom severity. Item 4 of the PHQ-15 (menstrual problems) was not deemed appropriate for the elderly Casper patient population and omitted from all questionnaires. Therefore the total possible PHQ-15 score will be 28.

### *CD-RISC 2*

The CD-RISC 2 is a 2-item short form of the full Connor-Davidson Resilience Scale (CD-RISC 25). It is a psychological resilience measure with specific items for bounce-back from adversity and adaptability to change. Agreement with the two items is scored from 0 to 4, resulting in a total score of 0 to 8, where a higher score indicates greater resilience.

### *Adverse Events*

Serious Adverse Events (SAEs), i.e. any deaths, unscheduled hospitalisations and any other medically important conditions were identified on an ongoing basis and documented on an SAE form. Outcome status and relatedness to the intervention (as assessed by a member of the trial management group) were recorded.

#### *Economic Evaluation*

Economic questionnaire items covered participants' health resource use, such as hospital visits and stays as well as use of further NHS and other health support services.

## Data Collection Schedule

Table 1: Data Collection Schedule

	Invitation	Baseline	Diagnostic Interview	4 month follow-up	12 month follow-up
Consent/Decline	•				
Demographic questionnaire	•				
Whooley questionnaire	•	•			
Physical health problems	•				
Falls questions	•				
PHQ-9		• 	• 	•	•
SF-12		•		•	•
EQ-5D		•		•	•
GAD-7		•		•	•
PHQ-15		•		•	•
CD-RISC 2		•		•	•
Medication questionnaire		•		•	•
M.I.N.I.			•		
Economic evaluation		•		•	•
Objective medication data		•		•	•

 PHQ-9 at baseline will be reported in the participant baseline characteristics

 PHQ-9 at diagnostic interview will be used as covariate in the analyses

## 5. Data

### Data Sources

- Case Report Forms (CRFs)
  - Decline Form
  - Background Information Form
  - Baseline Questionnaire
  - Four Month Follow-up Questionnaire
  - Twelve Month Follow-up Questionnaire
  
- Study Management Database
  - Number of Invites Sent
  - Consent and Randomisation Dates
  - Centre, Practice and GP Codes
  - Randomised Allocation Group
  - Case Manager Allocations
  - Questionnaire Return Dates
  - Status Changes (death, dropout from treatment, follow-up or trial)
  - M.I.N.I. Diagnostic Interview Responses and Outcome
  - PHQ-9 at Diagnostic Interview
  - Web Completed Questionnaire Data (baseline, four months, twelve months)
  
- Patient Case Management Information System (PC-MIS)
  - Collaborative Care Session Dates
  - Collaborative Care Completion Status
  - Collaborative Care Session Type (Phone or Face-to-face)
  
- Local Investigator Spreadsheets
  - Adverse Event Details

All data will be available in csv format before being imported to the statistical analysis software.

### Data Management and Verification

CRFs will be received in paper format by York Trials Unit and scanned in by the data management team. A copy of the CRFs with the variable names from the database is kept in the Trial Master File. Variable names of online data will match those of paper data.

Comprehensive data validation algorithms have been incorporated into the processing of each CRF, including checks for completeness, internal consistency as well as appropriate data formatting and range checks. The data management team will document any violations of these validation rules. At the end of the trial, a final dataset will be handed over to the trial statistician. The statistician will conduct further data checks including checks for duplicate responses and date chronology across questionnaires. The statistician will generate any derived variables as required. Any decision rules, data changes and assumptions made by the statistician following receipt of the final dataset from

data management will be documented in a Trial Assumptions Form. The statistician will not make any changes to the health economics data and release a copy of this together with cleaned demographics and selected outcomes to the trial health economist.

In the event of multiple questionnaire instances being available in paper and/or online format for a patient at the same follow-up time point, the earliest instance containing a minimum of one completed item of the primary outcome (PHQ-9) will be included in the analysis. The questionnaire dates will be based on the automatically logged completion date for web data and patient completed CRF completion date (if missing: date stamp of CRF return date) for paper data. Individual outcome questionnaires completed online will only be considered if completed on the same day as the PHQ-9.

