## **6. Analysis**

### **Principles**

All analyses will be conducted on intention to treat basis (ITT), including all randomised participants in the groups to which they were allocated. Any post randomisation exclusions will be referred to the independent statistician on the DMEC for approval. Analyses will be conducted in Stata version 13 or later, using 2-sided significance tests at the 5% significance level. Results will be presented with 95% confidence intervals where appropriate. The statistician conducting the analyses will remain blind to treatment group until the primary analysis is finalised and checked by the second statistician.

Any missing data will be reported for all predictor and outcome variables by trial arm and response rates compared. No imputations will be undertaken, and the impact of missing data will be explored as part of secondary analyses of the primary outcome.

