### **Secondary Analyses**

1) To explore the potential clustering within collaborative care case managers, descriptive statistics of the PHQ-9 at 4 months will be presented grouped by case manager in the intervention arm. The intra-cluster correlation coefficient (ICC) will be calculated to assess between-case-manager variability. The primary analysis will be repeated adjusting for the clustering by case manager by including case managers as a random effect.

2) Any baseline predictors of PHQ-9 scores at 4 months (age, gender, GAD-7, PHQ-15, mental health medication use and previous history of depression based on M.I.N.I. responses) will initially be identified by individual logistic regressions using  $p < 0.10$ , controlling for PHQ-9 at randomisation. Any remaining predictors from a combined regression will be included as covariates in the primary analysis model.

3) In order to investigate the impact of missing data, any baseline predictors of non-response at 4 months follow-up will be included as covariates in the primary analysis model. Non-response will be defined as the absence of a valid PHQ-9 score, and predictors will be identified initially by individual logistic regressions followed by a combined regression using  $p < 0.10$ .

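### The rule for choosing between duplicate questionnaires accepts one PHQ-9 item while scoring needs seven, so a scorable PHQ-9 can be set aside (minor)

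*SAP*

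**What the plan says.** Four parts of the SAP bear on this.

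- **Selection.** Data Management and Verification covers patients with several paper or online questionnaires at the same follow-up time point. It states that "the earliest instance containing a minimum of one completed item of the primary outcome (PHQ-9) will be included in the analysis".
- **Scoring.** The PHQ-9 entry under Outcomes says: "The PHQ-9 is a nine item depression scale". On incomplete responses it says: "Up to two missing questionnaire items are pro-rated, and no total scores are calculated for responses with more than two missing items".
- **Consequences of having no score.** In the third of the Secondary Analyses, "Non-response will be defined as the absence of a valid PHQ-9 score". Under Principles, "No imputations will be undertaken".
- **Who enters the model.** Under Analysis Population and Primary Analysis, a patient with complete baseline covariates needs a PHQ-9 at either 4 or 12 months.

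The SAP nowhere says what happens when the selected form cannot be scored but another form at the same time point can. It gives no fallback and no rule for combining forms.

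**The concern.** The selection rule and the scoring rule set different minimums for the same instrument. Applied as written, they can turn a primary outcome value that the trial holds into a missing one. The patient would then be modelled as a non-responder in the analysis meant to examine missing data, despite having returned a usable PHQ-9.

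This also works against a stated aim of the plan. The table of departures from the protocol justifies the mixed model by the wish to use as much of the available data as possible. A selection rule that sets aside a scorable PHQ-9 does the reverse, for no gain that the SAP describes.

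**Working it through.** **Step 1: compare the two thresholds.** The PHQ-9 has 9 items and at most 2 may be missing, so a total needs 9 − 2 = 7 items. Selection needs 1. The gap is 1 to 6 items.

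| PHQ-9 items on earliest form | Items on a later form, same time point | Result under the SAP rule |
|---|---|---|
| 0 | 7–9 | Earliest form passed over; later form used and scored |
| 1–6 | 7–9 | Earliest form used, no total; scorable form set aside |
| 1–6 | 0–6 | No total from either form, so no total is lost by the choice |
| 7–9 | any | Earliest form used and scored; no harm |

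Only the second row is a fault.

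**Step 2: follow a second-row patient.**

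- At 4 months the patient has no PHQ-9 total, nothing is imputed, and the patient is coded as a non-responder in the third secondary analysis.
- With a valid 12-month score and complete covariates, the patient stays in the mixed model but contributes no 4-month observation.
- Without a valid 12-month score, the patient leaves the primary analysis.
- If the fault occurs at 12 months instead, the secondary 12-month PHQ-9 value is lost and the 4-month value is unaffected.

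**Step 3: reproduce the SAP's sample size, as the base for sizing the loss.** Inputs from Sample Size: standardised effect 0.3, 80% power, two-sided 5%, ICC 0.02, caseload 20, loss to follow-up 26%.

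- Per arm: 2 × (1.96 + 0.8416)² / 0.3² = 174.4, so 175 per arm and 350 in total by the normal approximation. The SAP states 352, which is close enough.
- Design effect: 1 + (20 − 1) × 0.02 = 1.38. Then 352 × 1.38 = 485.8, so 486, as stated.
- Loss of 26%: 243 / 0.74 = 328.4, so 329 per arm and 658 in total, as stated.

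The plan's figures reproduce, and this point does not alter them.

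**Step 4: size the loss.** The SAP gives no frequency for second-row patients, so the number lost, k, is an assumption. The patients left are 658 × 0.74 − k = 486.92 − k. The effective number per arm is m = (486.92 − k) / (2 × 1.38). Power is Φ(0.3 × √(m/2) − 1.96).

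| k lost (share of 658) | Patients left | m | Power |
|---|---|---|---|
| 0 (0%) | 486.92 | 176.4 | 80.4% |
| 7 (about 1%) | 479.92 | 173.9 | 79.9% |
| 13 (about 2%) | 473.92 | 171.7 | 79.4% |
| 33 (about 5%) | 453.92 | 164.5 | 77.7% |

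At 1% to 2% the fall is 0.5 to 1.0 percentage points. The 5% row is an outer case and costs 2.8 points at full precision (80.45% to 77.65%). The sum treats each affected patient as wholly lost, so it gives no credit for a 12-month score in the model.

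**The case against.** The strongest reply is that the fault needs an unusual sequence of events, and most of that reply stands.

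- **Second pack.** A reader might infer that the reminder routinely produces such pairs, because "a reminder letter and second questionnaire pack were sent 21 days following the original mailing date". The Follow-up section makes that mailing conditional on the first pack not having come back. A patient who returned a part-filled pack does not trigger it. A pair arises only in edge cases, such as packs crossing in the post or a patient answering both on paper and online.
- **Part-filled web form.** This is possible but not established. Web data are dated by a logged completion date, and the SAP does not say whether an unfinished form receives one or enters the dataset.
- **Attrition.** A reader might link this to the rise in the loss allowance from 10% to 26%. Sample Size attributes that rise to interim recruitment figures and uneven dropout between arms, not to duplicate or unscorable forms. The selection rule is the same in both arms, and nothing in the SAP shows a bias in the treatment effect.
- **Same-day web rule.** A reader might extend the criticism to the sentence "Individual outcome questionnaires completed online will only be considered if completed on the same day as the PHQ-9", since no such limit is stated for paper. The SAP does not support that. A paper questionnaire has a single completion date, so its scales already share a date. The web rule aligns the other scales with the PHQ-9 and is a defensible choice.
- **Existing safeguards.** The statistician checks for duplicates, records decision rules in a Trial Assumptions Form, reports missing data by arm and adjusts for predictors of non-response. These make a loss more visible, but none recovers the scorable form. A rule affecting the primary outcome is better settled in the SAP than after the final dataset arrives.

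What remains is that the two written rules conflict in a defined case and no fallback is given.

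**Conclusion.** The point holds as a minor fault. Taking the earliest form is reasonable; the one-item threshold is the problem, because it is lower than the plan's own threshold for a score.

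It would be too strong to say that having several questionnaires makes a patient missing. The loss needs both an earliest form with 1 to 6 items and a later form with 7 to 9 at the same time point. It removes the score at that time point and not necessarily the patient.

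The number affected is unknown and probably small. The estimate of about one percentage point of power or less rests on an assumed 1% to 2% of 658 patients, on the SAP's own design effect and loss allowance, and on counting each affected patient as fully lost. The case for change is that the rule gives up primary outcome data needlessly, not that a large effect has been shown.

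**What to change.** In Data Management and Verification, replace the selection sentence with wording to this effect: where several questionnaires exist at a follow-up time point, use the earliest with a scorable PHQ-9 (at least 7 of 9 items completed); if none is scorable, use the earliest with any completed PHQ-9 item.

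This uses the scoring threshold already in the SAP and leaves the same-day web rule as it is. It costs one sentence and a small change to the selection code. The downside is that a few scores will come from a slightly later date than under the present rule. The change should be made before the follow-up data are examined by arm.

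### When a patient has two questionnaires at one time point, the selection rule can keep a PHQ-9 that cannot be scored and discard a later one that can

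*SAP*

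**What the plan says.** Four parts of the SAP bear on this.

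- **Selecting a copy** (5. Data, Data Management and Verification). The rule applies "In the event of multiple questionnaire instances being available in paper and/or online format for a patient at the same follow-up time point". In that case "the earliest instance containing a minimum of one completed item of the primary outcome (PHQ-9) will be included in the analysis". Copies are ordered by completion date. Online outcome questionnaires count only if they were completed on the day of the PHQ-9. No fallback to a later copy is given.
- **Scoring the PHQ-9** (4. Outcomes, PHQ-9). "The PHQ-9 is a nine item depression scale". For incomplete responses, "Up to two missing questionnaire items are pro-rated, and no total scores are calculated for responses with more than two missing items".
- **What the score is for** (4. Outcomes, Primary Outcome; 6. Analysis). The primary outcome is "Depression Severity and Symptomatology (PHQ-9) at 4 months post-randomisation". The mixed model uses the 4- and 12-month scores and takes in patients with a score at either. The Principles section rules out imputation. For the missing-data analysis at 4 months, "Non-response will be defined as the absence of a valid PHQ-9 score".
- **How duplicates arise** (3. Trial Design, Follow-up). For patients whose questionnaire has not come back, "a reminder letter and second questionnaire pack were sent 21 days following the original mailing date". The Data Sources section also lists questionnaires completed on the web.

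**The concern.** The threshold for choosing a copy (one item) is far below the threshold for using it (seven items). Nothing in the SAP makes the choice depend on whether the chosen copy can be scored. A patient who abandons a web form after a few PHQ-9 items and later completes the paper form would be represented by the abandoned attempt.

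The score lost is an observed value of the primary outcome measure. The plan does not impute it. At 4 months the patient is then labelled a non-responder in the third secondary analysis, and that label feeds the regressions that choose covariates for the missing-data check. This runs against the reason Table 2 gives for moving to a mixed model, which is to use as much of the available data as possible. Because the rule selects the whole questionnaire, SF-12, GAD-7 and medication answers on the later copy may be set aside as well.

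**Working it through.** **Step 1: compare the two thresholds.** The PHQ-9 has 9 items and at most 2 may be missing, so a total needs 9 − 2 = 7 completed items. For an earlier copy with a scorable later copy behind it:

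| Items completed on earlier copy | Selected? | Scorable? | Result |
|---|---|---|---|
| 0 | no | no | later copy used |
| 1 to 6 | yes | no | score lost, later copy discarded |
| 7 to 9 | yes | yes | earlier score used |

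The rule fails only in the middle row. A wholly blank earlier copy does no harm, but a copy with one to six items does.

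**Step 2: reproduce the plan's sample size**, so that the power figures start from its own base. Inputs from the Sample Size section: effect 0.3 SD, 80% power, two-sided 5%, ICC 0.02, caseload 20, loss 26%.

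- Before inflation: the normal approximation gives 175 per arm; the plan has 176 (352 in total), which agrees within one patient per arm.
- Design effect: 1 + (20 − 1) × 0.02 = 1.38.
- After clustering: 352 × 1.38 = 485.8, so 486 (243 per arm).
- With 10% loss: 486 / 0.90 = 540.
- With 26% loss: 486 / 0.74 = 656.8, so 657, or 658 as an even number.

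The plan's figures stand and are not in dispute.

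**Step 3: power if scorable patients are lost.** The SAP does not say how many patients would be affected, so the losses below are assumptions. Each affected patient is treated as wholly lost. With n per arm = (486 − lost) / 2,

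power = Φ( 0.3 / √(1.38 × 2 / n) − 1.96 ).

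| Assumed lost | n per arm | Power |
|---|---|---|
| 0 | 243 | 80.4% |
| 5 | 240.5 | 80.0% |
| 10 | 238 | 79.6% |
| 15 | 235.5 | 79.1% |

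For the first row: √(1.38 × 2 / 243) = 0.1066; 0.3 / 0.1066 = 2.815; 2.815 − 1.96 = 0.855; Φ(0.855) = 0.804.

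As an outer bound, suppose 5% of all 658 randomised patients (33) lost the score in this way. The number observed would be 658 × 0.74 − 32.9 = 454.0, and power 77.7%. Nothing in the SAP suggests a loss of that size.

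**Step 4: what happens to an affected patient.** Under Analysis Population and Primary Analysis, a patient with a valid PHQ-9 at either 4 or 12 months stays in the model, provided the baseline covariates are complete. Losing one score removes that observation. It removes the patient only if the other time point has no valid score either. Step 3 therefore overstates the loss for patients who keep the other score.

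**The case against.** The case for leaving the rule alone has several parts.

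- **The two rules do not contradict each other.** One picks a questionnaire and the other scores the PHQ-9 within it, so they can be applied in sequence. Taking the earliest copy also keeps the measurement close to its intended date. This stands: the fault is a low threshold with no fallback, not an inconsistency.
- **Harmful pairs need several things at once.** A reader might infer from the 21-day reminder that such pairs are likely. The Follow-up section does not support that, because the second pack goes only to patients whose first has not been returned. Someone who had already sent back a partly completed copy would not be sent another under that rule. What remains is crossed post, or paper and web used together, combined with 1 to 6 items on the earlier copy and at least 7 on the later. This stands: possible, but probably uncommon.
- **The loss is small.** A reader might also infer that affected patients drop out of the primary analysis, or that the treatment estimate is biased. The first holds only when the other time point has no valid score. For the second, nothing in the SAP indicates that such pairs would differ between arms.
- **Safeguards exist.** The statistician checks for duplicate responses and records decisions in a Trial Assumptions Form, and missing data are reported by arm. These make the loss partly visible but do not recover the score. Overriding the rule at that stage would mean departing from a prespecified rule with the data in hand.
- **A simple change of threshold has its own cost.** Moving the whole selection to the later copy could discard secondary scales that were complete on the first. This stands, and the fix has to deal with it.

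**Conclusion.** The point holds as a minor but real defect in a stated rule. Followed as written, the plan discards a valid PHQ-9 score whenever an earlier copy with 1 to 6 items precedes a scorable copy at the same time point. At 4 months it also counts that patient as a non-responder.

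The likely size is small. Frequency is unknown, and the power figures (80.4% falling to between 80.0% and 79.1%) rest on assumed losses of 5 to 15 patients, each treated as wholly lost. The argument for change is not power. An observed primary outcome value should not be thrown away when a short rewording, made before the data are seen, would keep it. The SAP supports neither a claim that this will happen often nor a claim that it biases the comparison between arms.

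**What to change.** Reword the duplicate rule in Data Management and Verification along these lines:

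- *Where several questionnaires exist for a patient at one follow-up point, use the earliest that gives a valid PHQ-9 total under the scoring rule (at least 7 of 9 items). If none does, use the earliest with any PHQ-9 item completed.*
- *A secondary scale that cannot be scored on the selected copy is taken from the earliest other copy at that time point on which it can be scored.*

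The second sentence prevents the change from discarding usable secondary data on the first copy. It needs an explicit exception to the requirement that online questionnaires be completed on the same day as the PHQ-9.

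The cost is a few lines of SAP text. A few scores will be dated somewhat later than the unusable first copy, and in a few patients the scales may come from different dates. The sample size does not change.
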